#### Part 1: Feasibility Trial

In order to ascertain the most appropriate parameters for the clinical trial, a feasibility trial will be run initially with 50 participants. Each of these first 50 participants will be entered into the raffle, regardless of whether they completed 75% of daily surveys.

When potential subjects click on articles relating to suicide, a pop-up asks patients whether they would like to participate in a study. If the user answers in the affirmative, a short questionnaire will screen in the appropriate subjects.

AT Condition: Participants in the AT condition will be provided at least 1 article per day during the 5-to-14-day initial study period by The Mighty platform management team. The articles provided in the AT

[figure not shown]
Condition will come from a predefined set of articles. This set of articles was chosen based on preliminary research by The Mighty platform management team suggesting that reading these articles was associated with a reduction in negative mood and/or self-injurious thoughts. The specific AT Condition articles will be provided before participants are recruited. Note: The articles in this condition are publicly posted articles/blog posts written by visitors to TheMighty.com. For a sample of articles see here: <https://themighty.com/topic/suicide/>. Participants in the AT condition will also receive a survey before and after each article. This survey will contain items assessing the following constructs: optimism, social connectedness, identification with the story's author, and suicidal ideation.

Control Condition: Participants in the Control condition will be sent emails with the same survey as those in the AT condition, but they will not receive articles.

After the feasibility trial is conducted, we will adjust the parameters of the research protocol such as length, timing for sending email, number of articles sent, etc. For example, it is plausible that most participants stop engaging after 5 days. If this is the case, the length of the study may be decreased from 14 days to as few as 5 days.

Part 2: Research Trial (See diagram below for timeline)

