The protocol for the actual research trial is nearly identical to the feasibility trial described above. We will recruit 500 patients total during the research trial. Patients will be randomized to either the AT or Control condition, with approximately 50% of the sample in each condition. Based on the results of the feasibility trial, we may adjust parameters in order to maximize meaningful engagement. Such parameters may include the number of articles sent, frequency of sending articles, timing of when articles are sent, etc. Additionally, all patients will receive a follow-up survey at 2 weeks after the 5-14 day intervention period in order to assess whether the effect of reading articles is sustained. These follow-up surveys will assess similar constructs to those assessed at baseline and during the intervention period. One week following administration of the follow-up surveys, participants in the Control condition will receive the same intervention (1 article assigned per day with pre- and post-article surveys) as those in the AT condition, as well as a final follow-up surveys 2 weeks after the intervention. The intent of this design is to allow those in the Control condition to also receive any benefits of the intervention.

***The below sections contain additional questions depending on the type of research that you are conducting and is meant to supplement the study overview. Please complete each section, as applicable.***

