## 7. CHARACTERISTICS OF THE STUDY POPULATION

7.1 Indicate the estimated number of participants, by subgroup if applicable. *If it is not possible to estimate the number of participants (e.g., open online survey), please indicate that it is not possible and provide an explanation of why it is not possible.*

For the initial feasibility trial, we will enroll 50 users in order to test out operations. After process optimization (adjusting timing of sending articles, number of articles sent, etc.), we plan to recruit a

total of 1000 participants for the RCT. Half (500 participants) will be randomized to the AT Condition, and half will be randomized to the Control Condition.

7.2 Describe the criteria for enrollment – Will you be limiting your enrollment to a certain age range, gender, people with certain health conditions, etc.? Please also describe any criteria that will exclude people from enrollment.

Enrollment Criteria: In order to qualify for the study, participants must report:

- having thought about suicide in the past 12 months, and
- that they are at least 18 years old
- English is primary language

Exclusion Criteria: Prospective participants will be excluded from the study if they report:

- a high level of suicide intent (as indicated by a 7 or greater on a 10-point scale of intent to act on suicidal thoughts)

7.3 Are there any potential vulnerable populations or individuals proposed for involvement in the research? (check all that apply)

- Children
- Wards of the State
- Prisoners/Detainees
- Pregnant Women
- Adults not Competent to Consent
- Non-English Speaking
- Employees of Harvard University (as a focus of the study)
- Undergraduate Students of Harvard University (as a focus of the study)
- Staff or students that are part of your lab or for whom you provide oversight
- Other – (see below):

*If “Other” please specify:*

---

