Title of study: Digital Narrative Bibliotherapy as a Scalable Intervention for Suicidal Thoughts

Document date: November 20, 2020

Document type: Statistical Analysis Plan

STATISTICAL ANALYSIS PLAN

We used an intent-to-treat design for all analyses, which were performed in RStudio.

Hypothesis 1: We predicted that the narrative bibliotherapy intervention would lead to lower ratings of the desire to die among participants assigned to the Treatment group, relative to those assigned to the Control group.

- **Analysis:** We used a mixed effects model as implemented in the *lme4* package to test whether participants in the Treatment group reported lower desire to die across the 14-day study period. This model included group (Treatment vs. Control) and day of the survey fixed effects. We also controlled for the effects of previous history of suicidal thoughts by including this measure as participant-level fixed effects.

Hypothesis 2: We predicted that the effect of the treatment would persist two weeks after the conclusion of the trial.

- **Analysis:** We used a *t*-test to examine group differences (Treatment vs. Control) in desire to die at the two-week follow up point.

Hypothesis 3: We predicted that participants who completed more days of the trial would report lower desire to die if they were assigned to the Treatment group (i.e. dose response effect).

- **Analysis:** We used a mixed effects model as implemented in the *lme4* package to tested the effect of the number of days of participation on participants' desire to die across the 14-day study period. This model included group and days of participation as participant-level fixed effects.

Hypothesis 4: We predicted that reductions in the desire to die resulting from reading suicide narratives to die would be attributable to increased feelings of optimism and connectedness.

- **Analysis:** We used mediation analysis as implemented in the *lavaan* package to examine the indirect effect of connectedness and optimism on the association between group assignment and desire to die.

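### The Hypothesis 3 dose-response model has no survey-day term, so if participants stop early, a fall in desire to die common to both arms is partly counted as an effect of days of participation

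*SAP*

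**What the plan says.** The SAP's Hypothesis 3 is that "participants who completed more days of the trial would report lower desire to die if they were assigned to the Treatment group", which it labels a dose-response effect. The analysis is a mixed effects model of "the effect of the number of days of participation on participants' desire to die across the 14-day study period". Its terms are given in one sentence: "This model included group and days of participation as participant-level fixed effects".

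The Hypothesis 1 model uses the same outcome over the same period but lists survey day: "This model included group (Treatment vs. Control) and day of the survey fixed effects". Neither a survey-day term nor a group-by-days interaction is listed for Hypothesis 3.

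On the pattern of participation, Protocol section 5.1 (Part 1: Feasibility Trial) says that "it is plausible that most participants stop engaging after 5 days". No rate is given.

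**The concern.** The exposure decides when the outcome is measured. Someone who leaves after 5 days is represented only by ratings from days 1 to 5, while someone who stays 14 days also contributes ratings from days 6 to 14. If desire to die drifts downward after enrolment for reasons unrelated to the articles, longer participants have lower average ratings simply because some of their ratings are later. Without survey day in the model, that difference has nowhere to go but the coefficient for total days.

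Some drift is possible. Participants are recruited as they open suicide-related articles (Protocol 5.1 and 8.1), which may be a worse moment than usual for them. The documents neither state nor quantify a drift. A rise over time would bias the coefficient the other way and could hide a real dose response.

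At stake is the dose-response claim. A significant days coefficient could be reported as support for the intervention when it reflects only the timing of the ratings.

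**Working it through.** The plan gives no effect size, SD or expected result for Hypothesis 3, so there is no stated figure to reproduce. The check is a derivation followed by simulation.

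**Inputs from the documents.** Model terms: group and total days (SAP, Hypothesis 3). Period: 14 days. Allocation: "with approximately 50% of the sample in each condition" (Protocol 5.1, Part 2). Sample size: "We will recruit 500 patients total during the research trial" in Protocol 5.1, but "total of 1000 participants for the RCT" in Protocol 7.1. That conflict is a separate matter, and both sizes were run.

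**Assumptions not in the documents.** Days completed uniform on 1 to 14; the SDs and falls shown below; two-sided 5% test; no treatment effect and no dose effect.

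**Derivation.** With consecutive participation for D days, mean survey day = (1 + 2 + ... + D)/D = (D+1)/2. If every rating changes by b per day, a participant's expected mean rating is a constant + b(D+1)/2. This is linear in D with slope b/2. The SDs do not enter the bias; they affect only how often it reaches significance.

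Example: a 1-point fall from day 1 to day 14 gives b = -1/13 = -0.077. For 14 days against 5 days, mean survey day is 7.5 against 3, a gap of 4.5 days. The spurious difference is 4.5 × 1/13 = 0.35 point.

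**Simulation 1.** N = 500, between-person SD 2.5, residual SD 1.5; two sets of runs, 300 and 400 per setting.

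| Shared fall over 14 days | b/2 | Days coefficient, model as written | False positives, model as written |
|---|---|---|---|
| none | 0 | | 5.7%; 6% |
| 1 point | -0.038 | -0.038; -0.039 | 25.7%; 28% |
| 2 points | -0.077 | -0.076; -0.074 | 73.3%; 74% |

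With survey day added, the coefficient is about zero and false positives are 3.3-4.7%.

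**Simulation 2.** Between-person SD 2, residual SD 1.5, 200 runs per setting.

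| Fall per day | N | Days coefficient as written | False positives as written | With survey day |
|---|---|---|---|---|
| 0 | 500 | 0.0005 | 3% | 3.5% |
| 0.05 | 500 | -0.0245 | 14% | 3.5% |
| 0.10 | 500 | -0.0495 | 57.5% | 3.5% |
| 0 | 1000 | 0.0021 | 4% | 4% |
| 0.05 | 1000 | -0.0229 | 28.5% | 4% |
| 0.10 | 1000 | -0.0479 | 79.5% | 4% |

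The coefficients match b/2 (-0.025 and -0.050). At 200 runs, a true 5% rate has a standard error of √(0.05 × 0.95/200) = 1.5 percentage points.

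**Boundaries, under the Simulation 2 assumptions.**
- Missed days scattered at random instead of early stopping: bias about zero, false positives 4-6%.
- Group-by-days interaction under early stopping with a shared fall: mean about zero, false positives 4.5-7%.
- Curved fall with only a linear day term (N = 500): the coefficient goes from -0.065 to -0.009 and false positives from 76% to 8.5%. A linear term is therefore not quite enough if the trend bends.

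**The case against.** The strongest objection is that a shared fall does not reproduce what Hypothesis 3 predicts. The prediction concerns the Treatment group. A shared fall gives the same slope in both arms and cancels in a group-by-days interaction. That is correct, and it rules out the stronger reading that natural improvement alone would confirm the hypothesis. But the listed model has no interaction. Its only dose coefficient is the slope pooled over both arms, which is the one that is biased. Even with an interaction, the Treatment-arm slope read on its own would still carry b/2.

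A reader might also infer that any general fall shows up as a dose response. The documents do not support that. Total days must track how late the ratings were made, which happens with early stopping and not with random gaps. The protocol calls early stopping plausible and no more.

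The size is assumed throughout. Entry requires suicidal thoughts in the past 12 months and excludes high intent (Protocol 7.2), so participants need not enter at a peak. This stands: the direction of the bias follows from the model, and its magnitude is unknown.

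A further argument is that the interaction also fails if the arm difference grows over time. In simulation, growth of 2 points over 14 days shifted the interaction by -0.082, with 29% rejection. With one article a day, however, growth as articles accumulate is close to the dose response that the hypothesis posits, so this is a question of interpretation and not a clear false positive.

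Finally, the SAP is brief and its list of terms may not be exhaustive. Since survey day is named for Hypothesis 1 and not for Hypothesis 3, the natural reading is that it was left out.

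**Conclusion.** The concern holds for the model as listed, if participants tend to stop early. A change of b per day common to both arms then adds b/2 to the days coefficient with no article effect. Under the assumed values for 500 participants, false positives are about 26-28% for a 1-point fall over 14 days and about 73-74% for a 2-point fall, against about 5% with survey day in the model. These rates depend on the assumed SDs, falls and uniform stopping pattern; the b/2 result needs only consecutive participation and a linear trend.

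The documents do not show that such a fall occurred or that a dose response is absent. The point concerns Hypothesis 3 only: the Hypothesis 1 model lists survey day. Nor would adding survey day make the days effect causal. Days completed is determined after randomisation and by the participants themselves, so less distressed people staying longer would look like a dose response under any version of this model.

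**What to change.** 1. In the Hypothesis 3 model keep total days and add day of survey, preferably as a categorical term (13 indicators for 14 days), so that a curved trend is also absorbed.
2. Add the group-by-days term and make it the test of Hypothesis 3, since the prediction is specific to the Treatment group.
3. Do not replace total days with days completed before each rating as a main effect. Under consecutive participation that count equals survey day minus 1, so a design with intercept, group, survey day and prior days has rank 3 of 4 and the effect cannot be estimated.
4. As a sensitivity analysis, relate total days and its interaction with group to desire to die at the two-week follow-up already used for Hypothesis 2, adjusted for a baseline or first-day rating where available. The protocol needs reconciling first: section 5.1 puts follow-up at two weeks and section 5.3 at four, and the battery in section 5.2 does not name a desire-to-die item.
5. State that the Hypothesis 3 result is observational.

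Items 1, 2 and 5 cost some SAP wording and, because the SAP is written in the past tense, probably one refit of existing data. An interaction is estimated less precisely than a pooled slope. Item 4 uses fewer ratings, so it is less precise, and it depends on who answers the follow-up survey.

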***If you chose “Other” please specify:***

11.3 What amount will the compensation be worth?

Compensation for the study will include entry into a raffle to win one of two \$250 checks. One check will be allocated to participants in the AT condition and the other to those in the Control condition.

11.4 Describe which participants will receive compensation and when the compensation will be given.

Participants in each condition (AT and Control) will be assigned one numbered token for each completed survey during the entire study period. Participants will need to complete 75% of the daily surveys in order to qualify for a raffle, in which one token from the each group will be randomly selected at the end of study (week 4 for AT condition; week 8 for the Control condition). The two owners of those tokens will be asked for their physical mailing address so we can send them each a \$250 check. If a winning participant is not able to provide a mailing address, they will not be eligible to win the \$250 check.

11.5 Will you provide partial compensation for participants who do not complete all the study procedures?

Yes (see below)

No

*If "Yes" please explain how partial compensation will be managed:*

**HRP-316 WORKSHEET: PAYMENT which may be found in the ESTR library provides an overview of items pertaining to payment that may be helpful to the study team.**

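### The Hypothesis 3 model has one days slope for both arms, so it cannot test the dose response it predicts in Treatment

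*SAP*

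**What the plan says.** SAP, Hypothesis 3, predicts that "participants who completed more days of the trial would report lower desire to die if they were assigned to the Treatment group" and calls this a dose response. Its analysis is an lme4 mixed model for the effect of number of days on desire to die over the 14 days: "This model included group and days of participation as participant-level fixed effects". The SAP states no interaction, arm-specific slope or Treatment-only fit, and the protocol has no analysis text for this hypothesis.

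Three other places matter:

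- Protocol 5.1, Part 1: Control participants get "the same survey as those in the AT condition, but they will not receive articles". Part 2 describes the research trial as almost the same as the feasibility trial.
- SAP, Hypothesis 1: "We also controlled for the effects of previous history of suicidal thoughts". Hypothesis 3 does not list this covariate.
- SAP, opening statement: "We used an intent-to-treat design for all analyses".

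**The concern.** The prediction is about one arm, but the listed model estimates one slope across both. In Treatment, a completed day brings an article. In Control it brings only a survey, so Control days are not a dose. A Control slope can arise from who keeps responding, from repeated surveying, or from reading outside the study.

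Days completed is also observed after randomisation. Protocol 5.1 expects that engagement may fall off after about 5 days, and Protocol 11.4 ties raffle entry to completing 75% of daily surveys in either arm. Days therefore measures retention as well as exposure.

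A published dose-response claim for a suicide-prevention intervention could then rest on a coefficient that does not separate article dose from who keeps answering surveys. The same coefficient could also hide a real dose response.

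**Working it through.** The plan gives no power, effect size or SD for Hypothesis 3, so there is no stated figure to reproduce.

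**1. Parameters.** The listed model is Y = a + g·Group + b·Days: three fixed-effect parameters and one slope b. Adding c·Group·Days gives four. The Control slope is then b, the Treatment slope b + c, and the between-arm difference c.

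**2. What the single slope estimates.** At participant level, b(planned) = (S_T·b_T + S_C·b_C)/(S_T + S_C), where S is the within-arm sum of squares of days. With 1:1 allocation (Protocol 5.1, Part 2) and the same spread of days, this is (b_T + b_C)/2.

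**3. Simple simulation.** Assumptions: days uniform on 1 to 14, so SD = √((14² − 1)/12) = 4.03; participant-level SD 1; two-sided 5%; 4,000 trials per scenario. N=500 comes from Protocol 5.1, Part 2, and N=1000 from Protocol 7.1.

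- SE of the planned slope at N=500: 1/(4.03 × √500) = 0.0111.
- SE of the interaction at N=500: √2/(4.03 × √250) = 0.0222, twice as large.

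| Slopes per day (T, C) | Planned estimate | Planned test rejects, N=500 / 1000 | Interaction rejects, N=500 / 1000 |
|---|---|---|---|
| −0.03, 0 | −0.015 | 27% / 48% | 27% / 47% |
| −0.03, −0.03 | −0.030 | 76% / 97% | 5% / 5% |
| −0.03, +0.03 | about 0 | 5% / 5% | 76% / 97% |

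In the first row the planned test has half the slope over half the SE, so detection is equal.

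**4. Simulation with retention selection.** Days 1–14 are generated from latent severity (SD 1) with an assumed correlation r, with one rating per completed day. A random participant intercept is assumed, because the SAP names no random effect. ICC runs from 0.3 to 0.8, with 4,000 trials per scenario. Slopes are in SD per SD of days.

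| Scenario | N | Planned test rejects | Interaction rejects |
|---|---|---|---|
| (a) r = −0.1 in both arms, no dose effect | 500 | 40–56% | 4–6% |
| (a) same | 1000 | 69–85% | 4–6% |
| (a) r = −0.2 in both arms, no dose effect | 500 | 94–99% | 4–6% |
| (a) same | 1000 | over 99% | 4–6% |
| (b) no selection, Treatment slope −0.30 | 500 | 75–90% | 74–89% |
| (c) r = +0.15 in both arms, Treatment slope −0.30 | 500 | 5–6% | 75–90% |

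Hand check of (a) at r = −0.1, ignoring within-person noise: z = 0.1 × √500 = 2.24, about 61% rejection; at N=1000, z = 3.16, about 89%. The simulated rates lie below these ceilings, as they should. In (c) the planned slope is 0.15 + (−0.30)/2 = 0, an exact cancellation.

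A run at ICC 0.6 with 60% of participants stopping by day 5 gave similar rates for (a) at N=500: planned 54% at r = −0.1 and 99% at r = −0.2; interaction 4–5%.

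**5. Limit of the interaction.** With r = −0.2 in Treatment only and no dose effect, the interaction rejects in 40–57% (N=500) and 70–85% (N=1000). A history covariate correlated 0.5 with severity lowers this to 30–44% and 54–74%. If history is related to days only through severity, its correlation with days is 0.5 × (−0.2) = −0.1. The remaining bias is then about (−0.2 + 0.5 × 0.1)/(1 − 0.01) = −0.15, against −0.20 without the covariate.

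**The case against.** The SAP is a short summary that leaves out even the random effects, so an interaction may have been fitted and not written down. That is possible. The text as it stands specifies none, and if one was fitted the remedy is a sentence.

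Without retention selection, the planned test finds a Treatment-only slope as often as the interaction does. This stands; what remains there is a halved estimate and no comparison with Control. The false-positive and masking cases need selection, whose sign and size the documents do not give. Scenario (c) is the exact-cancellation value: at r = +0.05 the planned slope would be 0.05 − 0.15 = −0.10, so masking would be partial.

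Power for the interaction depends on the assumed slope. A slope of −0.03 per day is 0.03 × 4.03 = 0.12 SD per SD of days, and detection is then only 27% at N=500 and 47% at N=1000.

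Hypothesis 3 is worded as a slope within Treatment, not as a steeper slope than Control. A slope difference alone could come from a rising Control slope with a flat Treatment slope. This is a fair point, and it is why both arm slopes must be reported.

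The evidence for unequal retention is thin. In the initial period only one arm has the extra burden: "Participants in the AT condition will also receive a survey before and after each article". The raffle draw differs too ("week 4 for AT condition; week 8 for the Control condition"), but Control's later draw fits its delayed intervention. These show that differential retention is possible, not that it occurs. Group does enter as assigned, so the intent-to-treat statement is not contradicted; it simply does not protect a comparison across days completed.

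**Conclusion.** The concern holds. Followed as written, the Hypothesis 3 analysis gives one slope averaged over an arm with articles and an arm without them, and has no parameter for the Treatment dose response. This follows from the listed terms alone.

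The size of the harm does depend on assumptions. A Treatment-only slope is halved if the arms are equal and have the same spread of days. Modest selection common to both arms can make the planned test significant in roughly half or more of trials with no dose effect, and selection in the other direction can hide a real one. The omitted history covariate is a secondary point. Hypotheses 1 and 2 are not affected, so this should be fixed but does not threaten the trial's main comparison.

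**What to change.** - Add the group-by-days interaction to the Hypothesis 3 model and make the slope difference (Treatment minus Control) the H3 test.
- Report both arm-specific slopes with confidence intervals. Describe the result as a Treatment dose response only if the Treatment slope itself is negative.
- Include the suicidal-history covariate already used for Hypothesis 1.
- State that days completed is post-randomisation, that the interaction stays biased if retention selection differs by arm, and that H3 is therefore an observational association outside the protection of the intent-to-treat statement.
- The SAP is written in the past tense. If the analysis has already been run, say whether an interaction was fitted, and label any changed test as post hoc.

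The cost is one model term, one existing covariate and a short limitation statement, with no new data. With equal arms the interaction has about twice the standard error of the pooled slope, and it does not remove arm-specific retention bias.

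### Hypothesis 3 relates ratings to total days completed, a self-selected post-randomisation total: this is not intent-to-treat, cannot test the Treatment-only slope, and can show a false dose response if worse mood shortens participation

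*SAP*

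**What the plan says.** The SAP opens with a statement that covers every analysis: "We used an intent-to-treat design for all analyses, which were performed in RStudio".

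Hypothesis 3 predicts that "participants who completed more days of the trial would report lower desire to die if they were assigned to the Treatment group", and labels this a dose response effect. The analysis is a mixed effects model of "the effect of the number of days of participation on participants' desire to die across the 14-day study period". Its listed terms are given in one sentence: "This model included group and days of participation as participant-level fixed effects". No group-by-days term, survey day or baseline covariate is listed. Adjustment for history appears under Hypothesis 1 only: "We also controlled for the effects of previous history of suicidal thoughts by including this measure as participant-level fixed effects".

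On stopping, the protocol (section 5.1, Part 1) says "it is plausible that most participants stop engaging after 5 days". Section 6.2 offers easy exit as a safeguard against distress from the survey questions. Section 11.4 makes raffle entry depend on completing 75% of the daily surveys. Neither document says whether mood affects stopping, or in which direction.

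**The concern.** Total days is known only once a person has sent a last survey, yet it is used to explain every rating from day 1 onward. It is an outcome of participation, not something that was randomised. If people with a stronger desire to die tend to leave sooner, long participation will go with low ratings even when the stories have no effect. A dose-response finding is usually read as strong causal support, so the trial could present a pattern of who stayed as evidence of what the stories did.

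Two problems need no assumption about mood. Conditioning on a post-randomisation variable conflicts with the blanket intent-to-treat statement. And a single days coefficient pooled over both arms cannot show that the slope exists in Treatment only, which is the hypothesis.

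**Working it through.** **Inputs from the documents.** The study period is 14 days and allocation is about 1:1. Total size is either 500 (Protocol 5.1, Part 2: "We will recruit 500 patients total during the research trial") or 1,000 (Protocol 7.1: "total of 1000 participants for the RCT"), so both were run. There is no figure in the plan to reproduce: no alpha, power, SD or dropout rate is stated for this analysis.

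**Assumptions.** Two-sided 5% level; outcome SD 1; within-person correlation 0.6; 90% chance per day of continuing (mean about 7.7 of 14 days); true story effect zero; 1,000 replicates per scenario; random-intercept model fitted by REML. The SAP does not list the random effects.

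**Step 1: the model as written.** For person *i* on day *t*, with group *G* and total days *D*:

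rating = α + β·G_i + γ·D_i + b_i + e_it

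If the stories do nothing, the rating is u_i + e_it, where u_i is the person's own level. Then γ estimates roughly Cov(D, u)/Var(D) within arm. This is zero only if stopping is unrelated to u. The hypothesis concerns the slope in Treatment, which needs γ + δ·G_i; no δ is listed.

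**Step 2: false dose response under the null.** Stopping follows logit P(continue) = ln(0.9/0.1) − ln(OR) × u_i/SD(u), the same in both arms. A false dose response is a negative γ with two-sided p < 0.05 (nominal 2.5% in that direction).

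| Stopping OR per SD of worse mood | Spurious slope (SD per day) | N = 500 | N = 1,000 |
|---|---|---|---|
| 1.0 | 0.000 | 2% | 3% |
| 1.1 | −0.012 | 35% | 57% |
| 1.2 | −0.023 | 84% | 99% |
| 1.5 | −0.048 | 100% | 100% |

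At an odds ratio of 1.2, the false gap between a one-day participant and a 14-day completer is 13 × 0.023 = 0.30 SD.

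If stopping depends on the latest rating instead, the rate at 1.2 with N = 500 is 76%. Fitting the Treatment arm alone gives 57% (N = 500) and 84% (N = 1,000) at 1.2. If worse mood keeps people in (odds ratio 1/1.5, N = 500), the slope has the opposite sign in 100% of trials and a false benefit never appears.

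**Step 3: the group coefficient adjusted for days.** Take an odds ratio of 1.5 in both arms and half the daily odds of continuing in Treatment. The group coefficient is then about −0.13 SD although the stories do nothing. It is significant in 45% (N = 500) or 72% (N = 1,000) of trials, against 4% when days is left out.

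**Step 4: adding group-by-days.** With equal mood-driven stopping, the interaction is falsely favourable in 2% to 3% of trials, which is nominal. With different stopping by arm it is not protected:
- Odds ratio 1.5 in Treatment and 1.2 in Control: 40% (N = 500) and 65% (N = 1,000).
- A second set of assumptions (between-person SD 1.0, residual SD 0.7, stopping log-odds 0.2 per unit of current rating in Treatment only, survey day added): about 35% to 73% over repeated runs at the two sizes. Here the total SD is √(1.0² + 0.7²) = 1.22, so the odds ratio is exp(0.2) = 1.22 per unit, or exp(0.2 × 1.22) = 1.28 per SD.

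**Step 5: a comparison that randomisation protects.** Group by survey day uses only assignment and the calendar. Under the second set of assumptions with no story effect, but with people having their own time trends (slope SD 0.05 to 0.10 per day), a random-intercept-only version rejected in about 12% to 41% of trials. With random slopes for day it rejected in 4% to 7%. It detected an immediate constant effect of −0.3 in only 4% to 6% of trials.

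**The case against.** The strongest reply is that the false positives rest on an assumption. A reader might infer that mood does decide who stops, and that the model will therefore report a dose response from inert stories. The documents do not support that. They expect disengagement and offer easy exit, but they also give a driver of completion unrelated to mood, the raffle threshold. With no link the error rate is nominal, and with the opposite link the model argues against the stories. This stands, and the claim has to be conditional.

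Second, if a group-by-days term was intended, that test is sound when mood drives stopping equally in both arms. This also stands. But the term is not listed, and equal stopping cannot be taken for granted: in Protocol 5.1 a Treatment day has an article with surveys before and after it, while a Control day has only a survey. How far stopping would differ is not documented.

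Third, everyone stays in the assigned group, and Hypotheses 1 and 2 do not use days completed. This limits the damage to Hypothesis 3. It does not make a coefficient conditional on total days an intent-to-treat contrast.

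A reader might also think that replacing total days with stories scheduled so far (survey day minus 1 in Treatment, 0 in Control) rescues a dose-response test. It does not. G × (day − 1) = G × day − G, so with group and survey day in the model it is exactly the group-by-survey-day interaction, and it contains nothing about the dose received.

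**Conclusion.** The Hypothesis 3 analysis is wrong as written and should be fixed. Two parts rest on the text alone: the analysis is not intent-to-treat although the SAP says all analyses are, and a main-effects model cannot test a slope predicted in one arm only.

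The third part is conditional. If worse mood shortens participation, even a weak link gives a false dose response often: 35% to 57% of trials at a stopping odds ratio of 1.1 per SD and 84% to 99% at 1.2, the lower figure for 500 participants in total and the higher for 1,000. These rates depend on the assumed variances and on about 10% stopping per day. The conflict over sample size does not change the conclusion. A group-by-days term repairs the mismatch with the hypothesis, but protects against false positives only if mood-driven stopping is the same in both arms.

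**What to change.** 1. Reword the SAP's opening statement so that intent-to-treat does not cover Hypothesis 3. Fit any total-days model with a group-by-days term and adjustment for history of suicidal thoughts. Report it as an exploratory, non-randomised association, and drop the dose response label.
2. For a comparison protected by randomisation, test group by survey day using assigned group, with survey day, history, and participant random intercepts and random slopes for day. Describe the result as divergence between arms over time, not as an effect of dose received.

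This needs no new data. The SAP is written in the past tense, so the change may mean re-analysis and relabelling. The trial gives up a causal dose-response statement. The group-by-day test has little power against an immediate, constant effect, and it still assumes that stopping depends only on ratings already observed.
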